2 STUDY OBJECTIVES

2.1 Primary Objective(s)

To describe changes in bone disease in femur and lumbar spine in Gaucher's disease patients treated with Velaglucerase alfa measured by MRI.

2.2 Secondary Objective(s)

- To describe the socio-demographic of patients;
- To describe the clinical evolution of patients (asthenia, abdominal pain, chronic bone pain, bone crises, hemorrhagic syndrome, hepatosplenomegaly, pulmonary, neurological,)
- To describe the evolution of the parameters measured by MRI
 - Bone alterations (spine, pelvis, femurs, tibias and other symptomatic localization)
 - Visceral involvement (liver, spleen)
- To describe the evolution of biological parameters

If possible, compare the evolution of MRI parameters between treatment-naive patients and patients previously treated with another specific treatment for Gaucher disease at the baseline MRI.

3 STUDY ENDPOINT

3.1 Primary Endpoint(s)

The primary endpoint is the change over time between the baseline MRI and the follow-up MRIs, of the BMB score (11) weighted at T1 and T2 and measured at the femur and lumbar spine .

3.2 Secondary Endpoint(s)

The secondary and exploratory endpoint(s) of this study are:

- socio-demographic characteristics: age, sex, occupation
- history of the disease and context of diagnosis: age at diagnosis, type of symptoms, exams that allowed the diagnosis and its confirmation, enzymatic assay value, genotype and presence or absence of family history
- medical history
- clinical evaluation criteria: weight (kg), height (cm), absence or presence (mild, moderate or severe) asthenia, abdominal pain, chronic bone pain, bone crises, syndrome bleeding, pulmonary impairment, neurological impairment
- clinical endpoints of liver and spleen:
 - Absence or presence of hepatomegaly, with the extent of the arrow (medio-clavicular line) (cm)
 - Absence or presence of splenomegaly, with the extent of the costal overhang (cm).-
- liver evaluation criteria and spleen MRI:
 - Absence or presence of hepatomegaly, with the extent of the arrow (medio-clavicular line) (cm)
 - Absence or presence of splenomegaly, with the extent of the costal overhang (cm)
 - Liver volume (m3)
 - Spleen volume (m3)
 - Presence or absence of myocardial, nodules, fibrosis, vesicular stones or other alterations.
- evaluation criteria of bone lesions by MRI (spine, pelvis, femurs, tibias and other symptomatic localization)

Absence or presence of bone lesions and their locations: bone infiltration, cortical thinning, osteonecrosis, bone infarction, stroke sequelae, vertebral compression fracture or other bone disease
- evaluation criteria of the biological parameters: hemoglobin (g/dl); leukocytes (cells/mm3); platelets (mm3); ACE (angiotensin converting enzyme (U/l); ferritin (mg/l); chitotriosidase (nmol/ h/ ml); CCL18 (ng/ml), vitamin D (nmol/L), vitamin B12 (pmol / l); SGOT / AST (U/l), SGPT / ALT (U/l), GGT (U/l), alkaline phosphatase (U/l), triglycerides (mmol/l), total cholesterol (mmol/l) gamma globulin (g/l) serum calcium (mmol/l) presence or absence of a monoclonal peak and the type if any

4 STUDY PLAN

4.1 Data collection and transmission

All data entered will be used for analysis purposes and results will be submitted to inform regulatory agencies. Patient care and management is freely determined by the participating physician, in the framework of an observational study reflecting the daily medical practice. The clinical data, the results of routine clinical and laboratory testing that are part of standard medical care for patients with Gaucher disease will be collected from the medical record of the patient :

- Socio-demographic characteristics
- History of the disease and context of diagnosis
- Medical background
- MRI: abdominal and bone, as defined below
- Clinical data available in the range from 3 months before or after each MRI
- Biological data available in the range from 3 months before or after each MRI
- Treatment with VPRIV® (velaglucerase alfa), including the doses and regimens

4.2 The MRI images collected during the study:

The MRIs performed in the patient's usual medical follow-up for its Gaucher disease (abdominal MRI (liver and spleen) and bone MRI (back injury pelvis, lower limbs) and / or whole-body MRI) will be collected. Among the MRIs available in the patient's medical records, MRIs will be collected the following:

- Reference MRI: MRI closest to the date of initiation of VPRIV® in the five years preceding the start of treatment or within three months after initiation of VPRIV®.
- MRIs of the retrospective phase of the study: All MRIs available between the reference MRI and the inclusion date of the patient.
- MRIs of the prospective phase of the study: all the MRIs that will be realized during the prospective phase of the study, that is to say, during the year following the date patient inclusion in the study.

4.3 Second lecture of the MRI

The collected MRIs will be subject to a second reading, which will be conducted centrally by a medical image processing center (BioClinica).

This second reading of MRIs will particularly provide quantitative data not available initially in the patient records, such as BMB score at the lumbar spine and femur, and liver and spleen volumes.

In case the second reading provides additional data to the first reading, as any new comments or discordant diagnosis, the investigating doctor will integrate these data as soon as it has knowledge of them in the medical care of the patient.

4.4 MRI collection and transmission

Except the data from the second reading of MRIs by BioClinica, all data defined above, will be collected in the case report of the study, from the patient's medical record.

For the second centralized reading of the MRIs, the MRIs will be transmitted as follows: the investigation center will make a copy on CD-ROM of each MRI collected for the study needs, and will replace the identity the patient by an identification number whose correspondence with the patient's identity is only known by the investigation center. This patient identification number will be predefined and attributed to the patient's MRI the patient is included in the study.

Copies of MRIs and coded will be sent securely at BioClinica center for analysis. In case of connection failure from the participating centers, MRI scans will be sent by post.

Data from this second reading by BioClinica will be retrieved for analysis. The results of the second reading by BioClinica will be forwarded to investigation center, which includes them the patient's record.

4.5 Data collection and transmission

As part of their routine practice, the practitioners working at the Gaucher Referent Centers in France collect a basic information form regarding the management of their Gaucher patients as well as the MRI data of these patients followed in these referent centers.

For the needs of the study, the Gaucher Referent Centers make a copy of the MRI Cd-Roms and and replace the person's identity on the copy by a code for which the Reference Centre alone has the chart for cross-referencing with the patient's identity. This code is made up of the first two letters of the surname and the first letter of the first name and a file number.

The imaging data thus made anonymous with respect to third parties are then transmitted to French Gaucher Treatment and Evaluation Committee "CETG" which in turn transfer them to BIOCLINICA, the radiological analysis centre. The latter is in charge of conducting standardised measurements of the volume of their hepatosplenomegaly as well as the characteristics of their bone disorders.

The resulting data are then sent to the CETG which in turn transfer these data to the Referent Gaucher Centers (practitioner) which includes them in the patient's monitoring file.

4.6 Indirectly personal character of data

The patient information is sent to the radiological analysis centre in an indirectly personal form comparable to that used in therapeutic trials, namely the patient's initials and a file number. Only the practitioner at the Gaucher Disease Reference Centre knows the correspondence between this number attributed to the patient and the patient's identity.

4.7 Justification of indirectly personal character

This indirectly personal character (initials and file number which only the practitioner can match with the patient's identity) allows the practitioner to record successive follow-ups of the patient without any risk of mistaking files.

4.8 Patients' rights protection

It is the responsibility of the Investigator to obtain written Informed Consent and assent, where applicable from study patients. All consent and assent documentation must be in accordance with applicable regulations and GCP. Each patient or the patient's legally authorised representative as applicable is requested to sign the Patient Informed Consent.

Form or a certified translation, if applicable after the patient has received and read (or been read) the written patient information and received an explanation of what the study involves, including but not limited to: the objectives, potential benefits and risk, inconveniences and the patient's rights and responsibilities. A copy of the informed consent and assent documentation (i.e., a complete set of patient information sheets and fully executed signature pages) must be given to the patient or the patient's legally authorised representative. If applicable, it is provided in a certified translation of the local language. Signed consent forms must remain in each patient's study file and must be available for verification at any time.

4.9 Overall Study Design and Plan

Figure 1. Overview of the Study Design

	0. Eligible patients (n= 40-50)	
	1. Patient inclusion (Written informed consent obtained)	
Retrospective data collection	
2. Retrospective data collection
 
The closest MRI conducted during the 5 years before the initiation of VPRIV® treatment or in the 3 months after the VPRIV® initiation is collected and corresponds to the reference MRI.
 
Clinical and biological data available 3 months before or after the reference MRI are collected
 
Medical history and clinical and biological data available, when VPRIV® treatment is initiated, are collected
 
Each MRI available since VPRIV® treatment initiation and patients inclusion is collected as well as clinical and biological data available 3 months before or after it
 
.....
 
MRI collected are anonymously sent to a central lab reading: MRI results data collection
	
Medical history
 
Clinical data
 
Laboratory data
 
VPRIV® treatment
 
MRI
 
..... VPRIV treatment
 
Centralized MRI reading:
 
 - Liver and spleen volumes - BMB score of the spine and femur
Prospective data collection	
3. Prospective follow-up:
 
For each MRI that will be conducted from the patient inclusion until the end of the one year follow up study, clinical and laboratory data available within the 3 months before the MRI and the 3 months after MRI are collected.
 
.....
 
.....
 
MRI collected are anonymously sent to a central lab reading: MRI results data collection
	
Clinical data
 
Laboratory data
 
VPRIV® treatment
 
MRI
 
.....
 
Centralized MRI reading:
 
 - Liver and spleen volumes - BMB score of the spine and femur
	
The study will last for one year from the date of the patient inclusion
 
The study is constituted of 2 phases: a retrospective and a prospective period
 
Phase I: Retrospective period
 
The retrospective period includes the period before VPRIV® treatment initiation until the beginning of this study..
 
Phase II: Prospective period
 
The prospective period will last for one year from the date of the patients inclusion
	

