4.12 Study Duration

The study is developed in conjunction with the French Referral Centers of Lysosomal Diseases, and the French Gaucher Treatment and Evaluation Committee (CETG: Comité d'Evaluation du Traitement de la maladie de Gaucher). It is a retro prospective observational study of the French cohort of patients with type 1 Gaucher disease treated with VPRIV® in everyday clinical practice.

It consists of two phases: a retrospective and a prospective phase with a 1 year inclusion period.

Phase I: retrospective phase

The retrospective period includes the period between the date of the baseline MRI to the patient's date of inclusion in the study. The reference MRI is defined as the closest MRI to the initiation of VPRIV®, within the past five years, or within three months after initiation of VPRIV®.

Phase II: prospective phase

Prospective period will be one year from the date of patient inclusion in the study.

The final MRI

MRI being performed in current practice every 2 years, the final MRI follow-up performed corresponds to those in the previous year or in the year following the patient's inclusion.

The duration of the study will be 2 years: a 1-year inclusion period to be sure to include all patients treated with VPRIV® (reviewed annually in consultation each year) and a prospective follow-up period of 1 year. Provisional timetable for the study:

CCTIRS / CNIL authorization	October 23, 2015
Inclusion of the first patient in the study	September 30, 2016
Inclusion of the last patient in the study	September 30, 2017
Last visit of the last patient	September 30, 2018
Study clinical report	January 31, 2019

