6.7 Efficacy and Effectiveness Assessments

For the closest MRI realized before the initiation of VPRIV® treatment and for each MRI which will be conducted during the prospective one year period, the following information will be recorded whenever they are available in patient's dossiers. Clinical and biological status will also be recorded when treatment was started and the patient included in the study.

- Spine and femur BMB score of T1 and T2 weighted,
- Marrow infiltration, bone infarction, osteonecrosis, pathological fractures (vertebral)

The clinical status:

***Retrospective and prospective observational study of MRI changes in bone and visceral lesions of patients with type 1
Gaucher disease treated with VPRIV® (velaglucerase alfa)***

- Height, weight
- Asthenia (absent / present : mild , moderate or severe), abdominal pain (absent / present : mild , moderate or severe), chronic pain in bone (absent / present : mild , moderate or severe), hemorrhagic syndrome (epistaxis, gingival bleeding, bruising, other rated : absent / present : mild , moderate or severe), lung disease, neurological disease

The biological status:

hemoglobin (g/dl); leukocytes (cells/mm³); platelets (mm³); ACE (angiotensin converting enzyme (U/l); ferritin (mg/l); chitotriosidase (nmol / h / ml); CCL18 (ng/ml), vitamin D (nmol/l), vitamin B12 (pmol/l); SGOT/AST (U/l), SGPT/ALT (U/l), GGT (U/l), alkaline phosphatase (U/l), triglycerides (mmol / l), total cholesterol (mmol/l) gamma globulin (g/l) serum calcium (mmol/l) presence or absence of a monoclonal peak and type if any.

The review will be done on the MRI that the treating physician has addressed for a central review radiological center via the CETG after blinding of the documents.

As previously, the quality of the MRI is evaluated and classified in three categories: Optimal, sub optimal and not assessable according the following definition:

- Optimal: Sufficient anatomical coverage, good image quality with no to minimal image artifacts and compliance with the imaging protocol
- Suboptimal: Sufficient anatomical coverage, presence of moderate image artifacts and/or minor deviations to the imaging protocol, with minimal impact on the analysis
- Not assessable: Insufficient anatomical coverage and/or presence of strong image artifacts and/or severe deviations to the imaging protocol, which would lead to an unreliable analysis.

Spleen/Liver:

TEST	DESCRIPTION	FORMAT/VALUES

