6.9 Concomitant Medications, Therapies, and Medical/Surgical Interventions Assessments

All medications, therapies/interventions administered to and medical/surgical procedures performed on the study subjects from the time of informed consent through the follow-up contact are regarded as concomitant and will be documented on the CRF.

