Not Related	No	The event can be readily explained by other factors such as the patient's underlying medical condition, concomitant therapy or accident and no obvious temporal or biologic relationship exists between the product and the event.

Outcome Categorisation

The outcome of AEs must be recorded during the course of the study in the CRF. Outcomes are as follows:

- Fatal
- Not Recovered/Not Resolved
- Recovered/Resolved
- Recovered/Resolved With Sequelae
- Recovering/Resolving
- Unknown

Symptoms of the Disease under Study

Symptoms of the disease under study should not be classed as ADRs as long as they are within the normal day-to-day fluctuation or expected progression of the disease. However, significant worsening of the symptoms should be recorded as an ADR.

Clinical Laboratory Evaluations

A change in the value of a safety laboratory investigation can represent an ADR if the change is clinically relevant or if, during treatment with the product, a shift of a parameter is observed from a normal value to an abnormal value, or a further worsening of an already abnormal value which is assessed to be associated with the use of VPRIV®. When evaluating such changes, the extent of deviation from the reference range, the duration until return to the reference range, either while continuing treatment or after the end of treatment with the product, and the range of variation of the respective parameter within its reference range, must be taken into consideration.

If, at the end of the observation period, there are abnormal laboratory values which were not present at the time of informed consent/patient enrolment, further clinical or laboratory investigations should be

***Retrospective and prospective observational study of MRI changes in bone and visceral lesions of patients with type 1
Gaucher disease treated with VPTRIV® (velaglucerase alfa)***

performed until the values return to within reference range or until a plausible explanation (e.g., concomitant disease) is found for the pathological laboratory values.

The Investigator should decide, based on the above criteria and the clinical condition of a patient, whether a change in a laboratory parameter is clinically significant and therefore represents an AE.

Pregnancy

All pregnancies are to be reported from the time informed consent is signed until the end of the study duration, as applicable.

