6.12 Removal of Patients from the Study

A patient's participation in the study may be discontinued at any time at the discretion of the Investigator. The following may be justifiable reasons for the Investigator to remove a patient from the study:

- Non-compliance, including failure to appear at one or more visits (or standard of care)
- The patient was erroneously included in the study
- The patient develops an exclusion criterion
- The patient suffers an intolerable adverse event
- The study is terminated by the Sponsor

The patient, the patient's parent(s), or the patient's legally authorized representative acting on behalf of the patient is free to withdraw consent and discontinue participation in the study at any time without prejudice to further treatment by the physician or at the institution. Discontinued patients should be followed according to medical practice standards.

If a patient or the patient's parent(s) or the patient's legally authorized representative(s) acting on behalf of the patient, discontinues participation in the study, or the patient is discontinued by the Investigator,

***Retrospective and prospective observational study of MRI changes in bone and visceral lesions of patients with type 1
Gaucher disease treated with VPRIV® (velaglucerase alfa)***

reasonable efforts will be made to follow the patient through the end of study assessments. The reason for refusal will be documented on the eCRF. Any adverse events (AE's) experienced up to the point of discontinuation must be documented on the AE eCRF. If AEs are present when the patient withdraws from the study, the patient will be re-evaluated within 30 days of withdrawal. All ongoing SAEs at the time of withdrawal will be followed until resolution.

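### After inclusion, clinical and laboratory values are scheduled only around an MRI, and none is fixed at the end of the prospective year

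*Protocol*

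**What the plan says.** The prospective box of Figure 1 (4.9, repeated in the synopsis and Appendix 2) makes the scan the trigger for collection: "For each MRI that will be conducted from the patient inclusion until the end of the one year follow up study". Around each such scan it asks for whatever clinical and laboratory values are on file up to 3 months either side. The data list in 4.1 uses the same window for every collected MRI: "Biological data available in the range from 3 months before or after each MRI".

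Section 4.12 sets the prospective period at one year from inclusion. It also describes imaging frequency: "MRI being performed in current practice every 2 years". It accepts a final MRI in the year before or the year after inclusion, so patients without a prospective MRI are expected.

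One provision is not tied to a scan. Section 6.7 states: "Clinical and biological status will also be recorded when treatment was started and the patient included in the study". There is no counterpart at the end of the year.

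Other sections assume a closing point. Section 6.10 on laboratory evaluations begins: "If, at the end of the observation period, there are abnormal laboratory values which were not present at the time of informed consent/patient enrolment". Section 6.9 records treatments "from the time of informed consent through the follow-up contact". Section 6.12 says that for discontinued patients "reasonable efforts will be made to follow the patient through the end of study assessments". The timetable in 4.12 dates the last patient's last visit one year after the last inclusion. None of these closing points is defined or given content.

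**The concern.** The secondary objectives (2.2) include the clinical evolution of patients and the evolution of biological parameters, and 8.6 compares these between study times. A one-year follow-up whose clinical and laboratory collection depends on a two-yearly examination leaves many patients with no scheduled value after the inclusion record.

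Those with a later value are the patients who happened to be scanned. Care is left to the physician, so scan timing could be related to how the patient is doing. The prospective evolution would then describe a selected subset.

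The same gap affects safety. Section 6.10 contrasts laboratory values at the end of observation with those at enrolment. The enrolment side is recorded under 6.7, but the end side has no scheduled record. ADRs are collected only in the prospective part, so it is also the only period for which a closing safety statement could be made.

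**Working it through.** The protocol gives no figure for the share of patients with a prospective MRI, so there is nothing to reproduce.

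**Inputs from the protocol**
- MRI interval in routine practice: 24 months (4.12).
- Prospective period: 12 months (4.12).
- Collection window: 3 months before to 3 months after each collected MRI (4.1, 4.9).
- MRIs collected: up to the end of the prospective year (4.2).
- Expected number of patients: 40-50 (8.2).

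**Assumption, not in the protocol.** MRIs come at a regular interval of T months, and inclusion falls at a random point in that cycle.

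**Formulas**
- No MRI in the prospective year: 1 − 12/T.
- No MRI-linked window after inclusion: 1 − 15/T. An MRI in the 3 months before inclusion also has a window that runs past inclusion, so 12 + 3 = 15 months of MRI dates count.
- No window reaching months 9-12: 1 − 6/T. The MRI must fall in months 6-12.
- No window covering month 12: 1 − 3/T. The MRI must fall in months 9-12.
- Negative values are set to 0.

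**At T = 24**
- 1 − 12/24 = 50%: 20 of 40 or 25 of 50 patients. The 95% binomial range is 14-26 of 40 or 18-32 of 50.
- 1 − 15/24 = 37.5%: 15 of 40 or about 19 of 50.
- 1 − 6/24 = 75%: 30 of 40 or about 38 of 50.
- 1 − 3/24 = 87.5%: 35 of 40 or about 44 of 50.

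**Sensitivity to the interval**

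| T (months) | No MRI in the year | No window after inclusion | No window reaching months 9-12 | No window covering month 12 |
|---|---|---|---|---|
| 12 | 0% | 0% | 50% | 75% |
| 18 | 33% | 17% | 67% | 83% |
| 24 | 50% | 37.5% | 75% | 87.5% |
| 30 | 60% | 50% | 80% | 90% |
| 36 | 67% | 58% | 83% | 92% |

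Even with yearly scans, which 4.12 does not describe, half or more of the patients would have no window late in the year. A window is also only an opportunity: within it, only values already available in the record are taken.

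**The case against.** The case on the other side has four parts.

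1. **Not everything depends on an MRI.** A reader might infer that about half the patients have no record of any kind after inclusion. The protocol does not support that. Section 6.7 records status at inclusion, 6.9 documents treatments and procedures from consent, and 6.10 collects ADRs and pregnancies from consent to the end of the study. This objection stands. What is missing is a scheduled clinical and laboratory value after the inclusion record.

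2. **ADR reporting is a separate, continuous process.** A reader might infer that patients without an MRI are never asked about ADRs. Whether the form has a closing page or a box for none depends on the CRF, which is not shown, and sites are monitored against source documents (7.2). That inference has to be dropped. What remains is that the protocol names no point at which each patient's ADR status is closed.

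3. **The laboratory provision in 6.10 instructs the investigator; it is not a database comparison.** It can be followed from the medical record, and patients are seen yearly. A reader might infer that it can be applied only to patients scanned late in the year, which is wrong. The gap lies in what the study data can show.

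4. **Anchoring collection to MRI is deliberate.** The primary objective concerns MRI, and 4.12 accommodates two-yearly imaging. That is reasonable for the BMB endpoint. It does not meet the secondary clinical and biological objectives for patients not scanned in the year, nor does it give content to the closing points named in 6.9, 6.10, 6.12 and the timetable.

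**Conclusion.** The point holds in limited form. After the inclusion record, clinical and laboratory values are scheduled only within 3 months of an MRI, and none is fixed at the end of the prospective year.

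With a regular 24-month interval, about 50% of patients have no prospective MRI, about 37.5% have no MRI-linked window after inclusion, and 75-88% have no scheduled laboratory capture near month 12. At 18 months these shares are 33%, 17% and 67-83%.

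The figures rest on a regular interval and on inclusion timing unrelated to MRI timing. If inclusions and scans both follow the annual consultation, the shares change. The 37.5% also takes the window of an MRI done just before inclusion as running past the inclusion date, as 4.1 reads; without that allowance the share is 50%.

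The primary BMB endpoint is unaffected. The consequence is incomplete, MRI-selected follow-up for the secondary clinical and biological objectives, and an end-of-observation laboratory value that the dataset usually cannot show. This is a worthwhile, inexpensive improvement to the collection schedule.

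**What to change.** In 4.1, 4.9, 6.7 and Appendix 2 (and the matching synopsis text), add one closing record per patient at the end of the prospective year, whether or not an MRI was done. Take it from the routine annual consultation mentioned in 4.12. It should hold:
- the available clinical and laboratory values nearest month 12, with their dates;
- VPRIV treatment status;
- ADRs since consent, including an explicit entry for none.

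State that this record is what 6.9 means by the follow-up contact, 6.12 by end of study assessments and the timetable by the last visit, and that it supplies the end-of-observation values in 6.10. If the CRF already has such a page, the protocol need only describe it and refer to it. Section 6.11 ends collection of serious ADRs at a 6-month study duration, so that passage must be reconciled with the one-year period for the closing date to be unambiguous.

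The cost is protocol wording, one extra CRF page per patient (40-50 pages) and a little data entry. No extra visit, test or MRI is needed, and values not available in routine care would simply be recorded as missing.
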